6.7 Pharmacodynamics Parameters

Not applicable

6.8 Research Biomarkers

Samples for determination of cardiovascular biomarkers (Table below) will be taken at the times presented in the study assessments schedule, section 6.1. Cardiovascular biomarkers are reported in the following table.

Panel Name	Biomarkers
Cardiovascular Biomarkers	Lipid profile (total cholesterol, low density lipoprotein cholesterol (LDL-C), high density lipoprotein cholesterol, (HDL- C), triglycerides)*
	hsTnI (high sensitive Troponin I) (ng/mL)
	hsCRP (High-sensitivity C-Reactive Protein) (mg/dL)
	NT-proBNP (N-Terminal Prohormone of Brain Natriuretic Peptide) (pmol/L)
	Lp(a)* (Lipoprotein a)
	ApoA1* (Apolipoprotein A)
	ApoB*

Table 6: Cardiovascular biomarkers

*Analysis will be performed at a local laboratory at or near to the Investigator site. Sample tubes and sample sizes may vary depending on laboratory method used and routine practice at the site.

TPCA025 Version 2 (based on TPQA036 Version 2) Original:

Copy:

Effective Date: 27th August 2017 Prior Effective Date: 21st December 2016

Sponsor:	AstraZeneca AB	Protocol/CIP Number:	D7550C00003
CIL Project Number:	40343		

Conversions to AZ preferred units for cardiovascular biomarkers performed at local laboratories will be applied where needed. Units and conversion factors are reported in the "Labcodes" version dated 16 May 2017 or higher. Other cardiological biomarkers and responder analysis of PD biomarkers, as well as genetic variations that may affect PK, PD, efficacy, safety and tolerability related to AZD5718 treatment will be referred in an exploratory SAP and results will be described in a separate report.

The exploratory endpoints concerning cardiovascular biomarkers are the change at visit 4 (4 weeks) and at visit 4c from Baseline. Baseline value is defined as in section 6.3.

6.9 Exploratory Variables

6.9.1 Carotid-femoral pulse wave velocity and brachial pulse wave analysis

The following variables from cfPWV/bPWA will be collected/derived at the times presented in the study assessments schedule, section 6.1:

- Augmentation index (%),
- Carotid-femoral pulse wave velocity (ms),
- Pulse pressure amplification (ratio) derived variable,
- Central pulse pressure (mmHg),
- Central blood pressure systolic (mmHg),
- Central blood pressure diastolic (mmHg),
- Brachial blood pressure systolic (mmHg),
- Brachial blood pressure diastolic (mmHg).

Two PWA measurements and two PWV measurements per scheduled measurement time point will be required and each measurement must meet all predefined quality control criteria defined in the SphygmoCor study manual (referred hereafter as "acceptable" measurements). If any measurement fails to meet any of the quality control criteria, additional measurements must be performed until two measurements of acceptable quality are obtained.

For the purpose of the analysis, only acceptable measurements (quality control=1) will be used. The average per visit for cfPWV/bPWA parameters will be calculated as follows:

- If two or more acceptable measurements are reported, the average of all the values will be used.
- If only one acceptable measurement is reported, it will be displayed for the average.
- If all measurements are missing, then the average will be missing

Pulse pressure amplification is a derived variable and will be calculated as:

(Brachial blood pressure systolic – Brachial blood pressure diastolic)/(Central blood pressure systolic – Central blood pressure diastolic). Note that central blood pressure systolic cannot physiologically equal central blood pressure diastolic; thus, the denominator cannot

Original:

TPCA025 Version 2 (based on TPQA036 Version 2) Copy:

Effective Date: 27th August 2017 Prior Effective Date: 21st December 2016

Sponsor:	AstraZeneca AB	Protocol/CIP Number:	D7550C00003
CIL Project Number:	40343		

equal 0. If one of the values used for calculating pulse pressure amplification is missing, then pulse pressure amplification will be missing.

The exploratory endpoints concerning cfPWV/bPWA are the change at visit 4 (4 weeks) and at visit 4c from Baseline. Baseline value is defined as in section 6.3.

6.9.2 Clinical Outcome Assessments

The following PRO questionnaires will be collected at the times presented in the study assessments schedule, section 6.1:

- SF-36 V2.
- EQ-5D-5L from EuroQol Group
- Rose Dyspnoea score
- FACIT-Fatigue scale

The exploratory endpoints for PRO questionnaires are the changes at visit 4 (4 weeks) and at visit 4c (12 weeks) from Baseline. Changes are calculated as the Visit value minus the Baseline value. Baseline is defined as described in section 6.3. The PRO questionnaires variables are described below:

SF-36 V2

SF-36 is a general well-validated questionnaire which encompasses eight health domains:

- 1. physical functioning,
- 2. role physical,
- 3. bodily pain,
- 4. general health,
- 5. vitality
- 6. social functioning,
- 7. role-emotional,
- 8. mental health.

It also includes a single item that provides an indication of perceived change in health called Reported Health Transition (item 2 "Compared to 1 week ago, your health now"). In addition, 2 component summary measures, a physical component summary (PCS) measure and a mental component summary (MCS) measure will be constructed and scored based on the 8 health domain scales.

Scoring the data for the 8 health domains and the 2 component summaries will be performed using PROC CoRE Software 1.5. The software uses 2009 U.S. population norms and applies a Missing Data Estimation method as follows:

• A health domain score (except the physical functioning domain) will be estimated provided that at least one non-missing response is available within that domain.

Original:

TPCA025 Version 2 (based on TPQA036 Version 2) Copy:

Effective Date: 27th August 2017 Prior Effective Date: 21st December 2016

Sponsor:	AstraZeneca AB	Protocol/CIP Number:	D7550C00003
CIL Project Number:	40343		

- For the physical functioning domain item response theory will be used to develop a model for estimates of the missing score.
- Regression methods are then applied to estimate the PCS and the MCS on the basis of the available domains.

The eight health domains, the perceived change in health and the 2 component summary measures will be included in the statistical analysis.

EQ-5D

The EQ-5D questionnaire has five dimensions: Mobility, Self-Care, Usual Activities, Pain/Discomfort, and Anxiety/Depression and each dimension has five response levels i.e., level 1=no problem or none; level 2=slight problems; level 3=moderate problems; level 4=severe problems; level 5= unable to perform activity.

Each of the 5 dimensions comprising the EQ-5D descriptive system is divided into 5 levels of perceived problems

- Level 1: indicating no problem
- Level 2: indicating slight problems
- Level 3: indicating moderate problems
- Level 4: indicating severe problems
- Level 5: indicating extreme problems

The overall EQ-5D index score will be calculated on the basis of the UK set of weights (Euroqol UK TTO - EQ-5D-5L crosswalk index values with SAS using the United Kingdom (UK) value set). There should be only one response for each dimension. Missing values are treated within the Euroqol UK TTO algorithm of calculation. Only the overall EQ-5D index score will be included in the statistical analysis.

Rose Dyspnoea

The Rose Dyspnoea questionnaire has 4 items which need to be answered as Yes (scored 1) or No (scored 0):

- Item 1: Do you get short of breath when hurrying on level ground or walking up a slight hill?
- Item 2: Do you get short of breath when walking with other people your own age on level ground?
- Item 3: Do you get short of breath when walking at your own pace on level ground?
- Item 4: Do you get short of breath when washing or dressing?

Each activity associated with dyspnoea is assigned 1 point. The overall rose dyspnoea score will be calculated as the sum of the 4 scores and will range from 0 to 4, with 0 indicating no dyspnoea with activity and increasing scores indicating more limitations due to dyspnoea. Missing data will be counted as 0. If at least two out of the four items will be missing, then the overall rose dyspnoea will be missing.

Only the overall rose dyspnoea score will be included in the statistical analysis.

TPCA025 Version 2 (based on TPQA036 Version 2) Original:

Copy:

Effective Date: 27th August 2017 Prior Effective Date: 21st December 2016

Sponsor:	AstraZeneca AB	Protocol/CIP Number:	D7550C00003
CIL Project Number:	40343		

FACIT - Fatigue

The FACIT-Fatigue scale is a 13-item questionnaire, and each questionnaire has one of the following responses: Not at all, A little bit, some-what, Quite a bit, Very much.

Responses should be coded as follows:

- Not at all = 0,
- A little bit = 1,
- Some-what = 2,
- Quite a bit = 3,
- Very much = 4.

All responses must be reversed by subtracting the response from "4" except the responses to subscale items 'I have energy' and 'I am able to do my usual activities' which should remain as scored above. All subscale items will be then summed, multiplied by the number of items in the subscale (i.e. 13), and then divided by the number of items answered. This will produce the prorated subscale score. The higher the score the better the quality of life.

If there will be missing data, prorating by subscale in this way will be acceptable as long as more than 50% of the items were answered (e.g., a minimum of 7 of 13 items). If 50% of the items or less are answered, the prorated subscale will be missing. Only the prorated subscale score will be included in the statistical analysis.

6.9.3 GRACE 2.0 score at baseline

GRACE score is an ACS Risk Calculator that provides the percentage probability of death or death/MI at time-points up to 3 years following admission with ACS.

Subjects will be assessed for GRACE 2.0 score (%) at baseline.

7. STATISTICAL METHODS

7.1 General Methodology

Data will be summarized using descriptive statistics, by treatment group which consist of AZD5718 AZD5718 and placebo, where the placebo group matches the loses respectively. Data will be summarized at each visit.

For continuous variables, descriptive statistics will include the number of subjects (n), mean, SD, median, minimum and maximum.

For log-normal variables, descriptive statistics will include n, mean, SD, median, minimum, maximum, geometric mean (GeoMean) and coefficient of variation (CV).

For categorical variables and unless otherwise specified, the number and percentages of subjects by categories will be tabulated. Percentages will be calculated based on the number of subjects with no missing data, i.e., will add up to 100%. Categories with count of zero will be not displayed.

Distribution:

Original:

Copy:

TPCA025 Version 2 (based on TPQA036 Version 2)

Sponsor:	AstraZeneca AB	Protocol/CIP Number:	D7550C00003
CIL Project Number:	40343		

For count variables descriptive statistics will be similar as for continuous variables.

All efficacy, exploratory and safety variables as well as PK plasma concentrations will be summarized by treatment group and at each visit as appropriate using descriptive statistics as above. For continuous variables, descriptive statistics will be summarized both for the observed values and the absolute changes from baseline.

Changes from baseline, in certain categorical variables will be summarized using shift tables. The number and percent of subjects within each treatment group will be generated for each category post-baseline by baseline category.

Decimal points will be presented as follow:

- If the original variable has 1 or less significant decimal points then Mean, Median, first quartile (Q1), third quartile (Q3), GeoMean, LSmean, CI of the LSmean will be rounded to one more decimal point than the original variable significant decimal points
- If the original variable has 2 or more significant decimal points then Mean, Median, first quartile (Q1), third quartile (Q3), GeoMean, LSmean, CI of the LSmean will be rounded to same decimal points than the original variable significant decimal points
- If the original variable has zero significant decimal points then the SD, SE will be rounded to one more decimal point than the mean
- If the original variable has one or more significant decimal points then the SD, SE will be rounded to the same decimal point than the mean
- Minimum, Maximum: same decimal points as the original variable significant decimal points
- %CV: two decimal points
- Percentage: one decimal point
- Ratio: two decimal points
- CI of the ratio: two decimal points
- N, n: Integer
- P-value: three decimal points (displayed as "<0.001" for p-values lower than 0.001)

For efficacy and exploratory variables, the following statistical models will be used:

Mixed Model Repeated Measures (MMRM)

Mixed Model Repeated Measures (MMRM) analysis using all available data.

Fixed factors of the model will be:

- treatment
- visit
- treatment*visit interaction

The covariates (considered also as fixed) will be:

- type of MI
- baseline value

Distribution:

Original:

Copy:

TPCA025 Version 2 (based on TPQA036 Version 2)

Sponsor:	AstraZeneca AB	Protocol/CIP Number:	D7550C00003
CIL Project Number:	40343		

Visit within subject will be considered as repeated measurements.

The model will use the SP (POW) structure for unequally spaced data variance-covariance matrix as default. Comparisons of AZD5718 versus placebo and AZD5718 versus placebo will be assessed within the same model.

The reportable results for Normal variables will be:

- Descriptive statistics of the change from baseline calculated as Visit value minus Baseline value for each group;
- The LSmeans and standard errors for each group;
- The difference between active groups and placebo (LSmeans) together with the CI of the difference
- P-value

The reportable results for log-Normal variables will be:

- Descriptive statistics of the change from baseline calculated as EXP[LN(Visit value) LN(Baseline value)], for each group
- Back transformed LS means (which correspond to the estimated ratio between visit and baseline) for each group
- The ratio between active groups and placebo together with the CI of the ratio;
- P-value

The ratio will be calculated as the exponent of the difference in LS means of the logarithmic transformation; the CI for the ratio will be calculated as the exponent of the CI of the difference of the logarithmic transformation. In case the model will not converge for any reasons, the following back-up solutions will be adopted sequentially:

- 1. The compound symmetry will be used instead of the SP (POW)
- 2. The variable will be analysed using the ANCOVA model described below instead of using the MRMM model.

ANCOVA

ANCOVA model using data from Visits 2 and 4.

Fixed factor of the model will be:

treatment

The covariates (considered also as fixed) will be:

- type of MI
- baseline value

Comparisons of AZD5718	versus placebo and AZD5718	versus placebo will
be assessed within the same m	odel.	al B

Original:

TPCA025 Version 2 (based on TPQA036 Version 2) Copy:

Effective Date: 27th August 2017 Prior Effective Date: 21st December 2016

Sponsor:	AstraZeneca AB	Protocol/CIP Number:	D7550C00003
CIL Project Number:	40343		

The reportable results for Normal variables will be:

- Descriptive statistics of the change from baseline calculated as Visit value minus Baseline value for each group
- The LSmeans and standard errors for each group
- The difference between active groups and placebo (LSmeans) together with the CI of the difference
- P-value

The reportable results for log-Normal variables will be:

- Descriptive statistics of the change from baseline calculated as EXP[LN(Visit value) LN(Baseline value)], for each group
- Back transformed LS means (which correspond to the estimated ratio between visit and baseline) for each group
- The ratio between active groups and placebo together with the CI of the ratio
- P-value

The ratio will be calculated as the exponent of the difference in LS means of the logarithmic transformations; the CI for the ratio will be calculated as the exponent of the CI of the difference of the logarithmic transformation.

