8.5.1 Analysis of the primary variable(s)

The primary efficacy variable will test the null hypothesis that patients given AZD5718 [REDACTED] have less than 80% inhibition of u-LTE₄ compared to placebo, versus the alternative hypothesis that patients given AZD5718 have equal or more than 80% inhibition of u-LTE₄ compared to placebo (one-sided confidence interval) at week 4.

The primary efficacy variable will be analysed as change from baseline using a repeated measures model with type of MI (STEMI vs NSTEMI), time from randomization (days), treatment and time treatment interaction as fixed effects with baseline value as covariate. The covariance structure will be spatial power law covariance structures (generalisation of an auto regressive covariance structure allowing for none equidistant time points). All available data from each patient will be used for the analysis. The analysis will be done on loge scale. However, the result will be back transformed to original scale.

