8.6.1 Analysis of primary efficacy variable

The primary efficacy endpoint is to test the null hypothesis that subjects given AZD5718 have less than 80% inhibition of creatinine-normalized u-LTE₄ at visit 4 compared to placebo.

The first secondary efficacy endpoint is to test the null hypothesis that subjects given AZD5718 have less than 80% inhibition of creatinine-normalized u-LTE₄ at visit 4c compared to placebo.

All the analyses will be performed based on the Efficacy Analysis Set. All the assessments related to the first variable are described in section 6.4.1.

For both the endpoints, the change in creatinine-normalized u-LTE₄ will be analysed using the Mixed Model Repeated Measures (MMRM) described in section 7.1 using data from visit 2, 3, 4 and 4c.

Creatinine-normalized u-LTE₄ is log-Normal distributed. The analysed change from Baseline is calculated as Visit value in log minus the Baseline value in log.

One-sided test will be used to compare the change from baseline observed in the active group, vs the change from baseline observed in the placebo group. Alpha level will be set at 0.05. The reportable results will be those for log-Normal variables.

Comparison of AZD5718 versus placebo will also be assessed within the same model.

For further details on the statistical model please refer to the Appendix 2 and to the table in Appendix 3.

Back-up solution for statistical model:

In case the model will not converge for any reasons, the following back-up solutions will be adopted sequentially:

- The compound symmetry will be used instead of the SP (POW);
- The primary efficacy variable will be analysed using the ANCOVA model described in section 7.1 for log-Normal variables instead of using the MRMM model.

In addition to the results above, the following will also be generated:

- Descriptive statistics by group for all visits, for the actual value and for the change from baseline. Change from baseline is calculated as Visit value minus Baseline value;
- Graphical representations of change from baseline (mean(SD)) over time and by groups;
- Forest plots based on the results of the two models.

Creatinine-normalized u-LTE4 will be also listed for Efficacy Analysis Set at each visit.

TPCA025 Version 2 (based on TPQA036 Version 2) Original:

Copy:

Effective Date: 27th August 2017 Prior Effective Date: 21st December 2016

Sponsor:	AstraZeneca AB	Protocol/CIP Number:	D7550C00003
CIL Project Number:	40343		

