8.6.2 Analysis of secondary efficacy variables

Change from baseline in CFVR

The second secondary efficacy endpoint is the change from baseline in CFVR at Visit 4c.

The null hypothesis of no increase in CFVR in subjects given AZD5718 compared to placebo will be tested.

The third secondary efficacy endpoint is the change from baseline in CFVR at Visit 4.

The null hypothesis of no increase in CFVR in subjects given AZD5718 compared to placebo will be tested.

All the analyses will be performed based on the Efficacy Analysis Set. All the assessments related to the secondary variables are described in section 6.4.2.

Both the second and third secondary endpoints will be analysed using the Mixed Model Repeated Measures (MMRM) described in section 7.1 using data from visit 2, 4 and 4c.

CFVR is log-Normal distributed. The analysed change from Baseline is calculated as Visit value in log minus the Baseline value in log.

One-sided test will be used to compare the change from baseline observed in the active group, vs the change from baseline observed in the placebo group. Alpha level will be set at 0.05. The reportable results will be those for log-Normal variables.

Comparison of AZD5718 versus placebo will also be assessed within the same model.

For further details on the statistical model please refer to the Appendix 2 and to the table in Appendix 3.

In addition to the results above, the following will also be generated:

- Descriptive statistics by group for all visits, for the actual value and for the change from baseline. Change from baseline is calculated as Visit value minus Baseline value;
- Graphical representations of change from baseline (mean(SD)) over time and by groups;
- Forest plots based on the results of the two models.

CFVR will be also listed for Efficacy Analysis Set at each visit.

A sensitivity analysis may be performed as detailed in section 7.2.

Distribution:

Original:

Copy:

TPCA025 Version 2 (based on TPQA036 Version 2) Effective Date: 27th August 2017 Prior Effective Date: 21st December 2016

Sponsor:	AstraZeneca AB	Protocol/CIP Number:	D7550C00003
CIL Project Number:	40343		

Other secondary variables

The other secondary endpoints related to all other secondary variables are the changes from baseline at Visit 4. The exploratory endpoints related to all other secondary variables are the changes from baseline at Visit 4c.

The other secondary variables are:

- LAD resting mean diastolic flow velocity

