Appendix 2 Statistical analysis and programming details

Mixed Model with Repeated Measures (MMRM) – primary and first secondary endpoints (change at visit 4 and 4c on Creatinine normalized uLTE₄):

The SAS code used to implement this test will be similar to that shown below:

PROC MIXED data=dataset COVTEST NOCLPRINT METHOD=REML; CLASS Trt Mi Subject visit; MODEL Ch=Trt visit trt*visit MI Base / SOLUTION ddfm=KR; REPEATED Visit / TYPE=SP(POW)(awtarget) SUB=Subject; LSMESTIMATE trt*visit 'change at week X - AZD5718 vs placebo' 0 -1 0 0 1 0 / lower cl testvalue= -1.609437912 /* corresponding to ln(0.2) */; RUN;

Where awtarget is the expected day of visit.

Mixed Model with Repeated Measures (MMRM) – second and third secondary endpoints (change at visit 4 and 4c on CFVR):

The SAS code used to implement this test will be similar to that shown below:

PROC MIXED data=dataset COVTEST NOCLPRINT METHOD=REML; CLASS Trt Mi Subject visit; MODEL Ch=Trt visit trt*visit MI Base / SOLUTION ddfm=KR; REPEATED Visit / TYPE=SP(POW)(awtarget) SUB=Subject; LSMESTIMATE trt*visit 'change at week X - AZD5718 vs placebo' -1 0 1 0/ upper cl; RUN;

Where awtarget is the expected day of visit.

Mixed Model with Repeated Measures (MMRM) – change at visit 4 and 4c on Other secondary variables, all exploratory variables and cardiovascular biomarkers:

The SAS code used to implement this test will be similar to that shown below:

PROC MIXED data=dataset COVTEST NOCLPRINT METHOD=REML; CLASS Trt Mi Subject visit; MODEL Ch=Trt visit trt*visit MI Baseline / SOLUTION ddfm=KR; REPEATED Visit / TYPE=SP(POW)(awtarget) SUB=Subject; LSMESTIMATE trt*visit ' change at week 4c - AZD5718 vs placebo' -1 0 1 0 / cl ; RUN;

Distribution:

Original:

Copy:

TPCA025 Version 2 (based on TPQA036 Version 2)

Sponsor:	AstraZeneca AB	Protocol/CIP Number:	D7550C00003
CIL Project Number:	40343		

Where awtarget is the expected day of visit.

ANCOVA model – change at visit 4 on all variables except cardiovascular biomarkers at first Interim analysis:

The SAS code used to implement this test will be similar to that shown below:

PROC MIXED data=dataset; CLASS Trt MI; MODEL Ch= Trt MI Base; LSMESTIMATE trt ' change at week 4 – AZD5718 ng vs Placebo' -1 1 / cl ; RUN;

NB: LSMESTIMATE statement must be adapted based on data used in the model.

Distribution:

Original:

Copy:

TPCA025 Version 2 (based on TPQA036 Version 2) Effective Date: 27th August 2017 Prior Effective Date: 21st December 2016

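### The last-resort ANCOVA holds no week-12 data and so cannot test the week-12 endpoints; separately, the CFVR model assumes one variance for weeks 4 and 12, which a pre-specified sensitivity analysis would cover

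*SAP*

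**What the plan says.** **Covariance.** SAP 7.1 states: "The model will use the SP (POW) structure for unequally spaced data variance-covariance matrix as default". The Appendix 2 code agrees ("REPEATED Visit / TYPE=SP(POW)(awtarget) SUB=Subject") and has no option for visit-specific variances. Protocol 8.5.1 describes the structure as a "generalisation of an auto regressive covariance structure allowing for none equidistant time points", and Protocol 8.5.2 carries the same model over to CFVR. SAP 8.6.2 analyses CFVR with the mixed model "described in section 7.1 using data from visit 2, 4 and 4c", which means two post-baseline visits.

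**Fallbacks.** If the model does not converge, SAP 7.1 moves to compound symmetry and then to the ANCOVA. It defines the latter as an "ANCOVA model using data from Visits 2 and 4". SAP 8.6.1, which covers u-LTE4 at both Visit 4 and Visit 4c, repeats this: "The primary efficacy variable will be analysed using the ANCOVA model described in section 7.1 for log-Normal variables". SAP 8.6.2 gives CFVR no fallback of its own, so CFVR takes the one in 7.1. Appendix 2 presents the ANCOVA code as the model for "change at visit 4 on all variables except cardiovascular biomarkers at first Interim analysis".

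**Hierarchy and planning values.** SAP 7.6 tests u-LTE4 at week 4, u-LTE4 at week 12, CFVR at week 12 and CFVR at week 4, each one-sided at 5%, and stops at the first failure. Protocol 8.2 and SAP 4.5 give one CFVR coefficient of variation, 30%, not tied to a visit.

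**The concern.** An ANCOVA built for the first interim, when week 4 was the visit of interest, now also stands as the last fallback for a final analysis in which two of the four ordered endpoints are at week 12. It contains no observation from that visit.

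The covariance point is different in kind. With only two post-baseline CFVR visits there is a single interval, so unequal spacing gives no reason to prefer the spatial power structure. What remains is one variance and one correlation. Compound symmetry is the same CFVR model whenever the correlation is non-negative, so no pre-specified step lets the two SDs differ. If they do differ, the standard error of the week-12 contrast is too small or too large. That matters because week-12 CFVR is the stated reason for raising enrolment to about 138, and week-4 CFVR can be claimed only after it.

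**Working it through.** **A. Fallback 2 against the hierarchy**

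| Link | Endpoint | Defined by an ANCOVA on Visits 2 and 4? |
|---|---|---|
| 1 | u-LTE4, week 4 | Yes |
| 2 | u-LTE4, week 12 | No, needs Visit 4c |
| 3 | CFVR, week 12 | No, needs Visit 4c |
| 4 | CFVR, week 4 | Computable, but reached only through link 3 |

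If fallback 2 is reached for u-LTE4, link 2 has no result and links 3 and 4 have no defined gate. If it is reached for CFVR, link 3 has no result and link 4 has no gate.

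**B. The plan's own CFVR figure**

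The log SD is sqrt(ln(1 + 0.30²)) = sqrt(0.0862) = 0.2936, and the effect is ln 1.2 = 0.1823. Then n per arm = 2 × (1.645 + 0.842)² × 0.0862 / 0.1823² = 32.1, rounded up to 33. Power at 33 is 81.0% (normal) or 80.3% (noncentral t). 33/0.82 = 40.2, matching about 40 randomized. The plan's figure reproduces.

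**C. Size of the week-12 CFVR test under one variance**

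Assumed evaluable numbers per main arm, with 18% loss:

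- Week 4: 138 × 2/5 × 0.82 = 45.
- Week 12: 100 × 2/5 × 0.82 = 33.

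Let r be the week-12/week-4 SD ratio. It is an assumption and is not in the documents. The pooled variance relative to week 4 is V = (45 + 33r²)/78, and size = 1 − Φ(1.645 × sqrt(V)/r). For r = 1.4, V = (45 + 64.68)/78 = 1.406, sqrt(V)/r = 0.847, critical value 1.393, size 8.2%.

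| r | V | Size, closed form | Size, simulated (residual correlation 0.3 / 0.6) |
|---|---|---|---|
| 0.8 | 0.848 | 2.9% | 2.9 / 2.9% |
| 0.9 | 0.920 | 4.0% | 3.9 / 4.0% |
| 1.0 | 1.000 | 5.0% | 5.1 / 5.0% |
| 1.1 | 1.089 | 5.9% | 5.9 / 6.0% |
| 1.2 | 1.186 | 6.8% | 6.7 / 6.4% |
| 1.3 | 1.292 | 7.5% | 7.6 / 7.6% |
| 1.4 | 1.406 | 8.2% | 8.3 / 8.0% |

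The simulation fits the SAP model (three arms, type of MI, baseline, REML, Kenward-Roger) in 40,000 runs per case, with Monte Carlo SE about 0.11 points. An unstructured covariance fitted to the same data gave 4.7 to 5.1% at week 12 throughout. The split matters little: with equal numbers at both visits, sizes at r = 1.1 and 1.4 are 5.8% and 7.6%; with 45 and 28 they are 6.0% and 8.5%.

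**D. Week-12 power for a 20% increase (normal approximation)**

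With week-12 SD 0.2936 and 33 per arm, the standardized effect is 0.1823/(0.2936 × sqrt(2/33)) = 2.52. Visit-specific power is Φ(2.52 − 1.645) = 81.0%. At r = 0.8 the common-variance critical value is 1.893, so power is Φ(0.63) = 73.6%.

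| Which SD equals the planned value | r | One variance | Visit-specific | Loss (points) |
|---|---|---|---|---|
| Week 12 | 0.8 | 73.6% | 81.0% | 7.4 |
| Week 12 | 0.9 | 77.9% | 81.0% | 3.1 |
| Week 4 | 0.8 | 89.6% | 93.4% | 3.8 |
| Week 4 | 0.9 | 85.3% | 87.7% | 2.4 |

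**E. The same assumption for u-LTE4**

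Assume 45, 45 and 33 per arm at Visits 3, 4 and 4c, with only the week-4 SD differing, by a factor k. At the 80% boundary the week-4 size is 1 − Φ(1.645 × sqrt((45k² + 78)/123)/k). This gives 6.0%, 7.0% and 8.6% at k = 1.1, 1.2 and 1.4. The planned effect lies ln(0.20/0.04) = ln 5 = 1.609 log units beyond that boundary.

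**The case against.** **On the covariance.** Spatial power is pre-specified in the protocol and the SAP follows it. Every size away from 5% above comes from an SD ratio that the documents do not contain, and 1.4 means the variance nearly doubles (1.4² = 1.96). At 1.1 the excess is about 1 point. CFVR is summarized by visit, so a marked difference in SD would be seen. All of this stands, and it is why the point is a robustness improvement. Visible SDs do not by themselves change the test, however, because no rule links them to the model.

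**On changing the default.** The plan places two unblinded CFVR interims before the final analysis, and the second uses this same mixed model. A new default for a key secondary endpoint after those looks has a credibility cost. This stands too; a sensitivity analysis avoids it.

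**On the fallback.** Two mixed models must fail first, and for CFVR each has only two covariance parameters. An untested link cannot by itself produce a false claim. Both statements are right and they limit the consequence. The Appendix 2 note about adapting the estimate statement concerns contrasts; it adds no Visit 4c data.

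**Readings that go too far.** A reader might infer that the CFVR error rate is inflated. The documents do not show that: one CV with no visit attached leaves equal SDs entirely possible. A reader might also infer that the primary u-LTE4 test is immune. It is not, since the same single variance covers Visits 3, 4 and 4c. What protects its power is the planned margin, 96% expected inhibition against the 80% threshold.

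**Conclusion.** **Fallback 2** is wrong as written, and this needs no assumption. It cannot test either week-12 endpoint, and the links after an untested one have no defined gate. The event is remote.

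**The single CFVR variance** is an unprotected assumption, not an error. If the SDs are equal the week-12 test holds 5%. If the week-12 SD is 1.1 to 1.4 times the week-4 SD, size is about 6 to 8%. If it is 0.8 to 0.9 times, size is about 3 to 4%. Power at 0.8 to 0.9 is then about 3 to 7 points lower than with visit-specific variances if the week-12 SD is as planned (about 74 to 78%), or about 2 to 4 points lower and still above 80% if the week-4 SD is as planned. These figures rest on the assumed ratios and the assumed 45/33 split; the split and the correlation matter little.

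With no CFVR effect at either visit, the week-12 size is the chance of a false CFVR claim only if both u-LTE4 links pass; otherwise it is an upper bound.

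**What to change.** 1. **Correct fallback 2** in SAP 7.1 and 8.6.1. Define it as a per-visit ANCOVA using Visit 2 and the visit being tested, so Visit 4c for the week-12 endpoints, for both u-LTE4 and CFVR. Align the Appendix 2 label and code. This takes a sentence and a few lines of code and has no statistical cost.

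2. **Pre-specify a sensitivity analysis** for the two CFVR endpoints with `TYPE=UN` and `DDFM=KR` (three covariance parameters instead of two). State that the hierarchical decision stays with the default model. SAP 7.2 already pre-specifies a sensitivity analysis for the four ordered endpoints, so this fits beside it.

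3. **Optional: make the unstructured covariance the CFVR default**, with spatial power as the sensitivity analysis. Simulated week-12 power falls by about 0.3 points if the variances are equal. This departs from Protocol 8.5.1 and 8.5.2, so it needs a documented decision by blinded staff before final unblinding.

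Record whichever changes are made in SAP 5.2, which already keeps the unblinded team out of amendments after the first interim.
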